3.2.3. Exploratory

Immunogenicity:

- Maternal immunogenicity cofactors for maternal and neonatal anti-PT antibody responses following intrapartum BOOSTRIX: Maternal age (18-29, 30-39 years old), parity (primiparous vs. multiparous), GA at time of vaccination (14-17, 18-21, 22-26 weeks), GA at time of delivery (28-32, 33-36, 37 or more weeks), and infant birthweight as potential independent associations with PT GMC.
- Maternal secretory immunity: GMC of breast milk IgG and IgA antibodies to Tdap vaccine antigens (PT, FHA, PRN, tetanus, diphtheria) as measured by ELISA in women at the time of delivery, at 6 weeks after delivery, at 10 weeks (in ½ of women) or 18 weeks (in ½ of women) after delivery, and 6 months after delivery after intrapartum receipt of BOOSTRIX versus Td.
- Maternal cytokine responses: Cytokines produced by peripheral blood cells stimulated with DTwP vaccine antigens, as measured by multiplex assays, in women before and one month after receiving Tdap. Cytokines measured will include: Interferon (IFN)- γ , Inerleukin (IL)-10, IL-12p70, IL-12/IL-23p40, IL-13, IL-15, IL-16, IL-17A, IL-1 α , IL-1 β , IL-2, IL-4, IL-5, IL-6, IL-7, IL-8, Tumor Necrosis Factor (TNF)- α , and TNF- β .
- Infant cytokine responses: Cytokines produced by infant peripheral blood cells stimulated with DTwP antigens from infants whose mothers received intrapartum BOOSTRIX versus Td, measured by multiplex assays before the first dose (or umbilical cord blood), one month after the first dose of DTwP (~10 weeks of age, ½ of subjects), one month after the last dose of study vaccine (approximately 18 weeks, ½ of subjects), and at 6 months of age. Cytokines measured will include: IFN- γ , IL-10, IL-12p70, IL-12/IL-23p40, IL-13, IL-15, IL-16, IL-17A, IL-1 α , IL-1 β , IL-2, IL-4, IL-5, IL-6, IL-7, IL-8, TNF- α , and TNF- β .

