## 8.3. Exploratory Immunogenicity Analyses

### 8.3.1. Maternal immunogenicity cofactors for maternal and neonatal anti-PT antibody responses following intrapartum BOOSTRIX

Summaries and analysis of immunogenicity data will be presented for maternal and infant subjects in the BOOSTRIX group for anti-PT antibody responses at time of delivery or birth, as applicable. Serum IgG antibody concentrations to PT will be summarized by maternal age (18-29, 30-39 years old), parity (primiparous vs multiparous), GA at time of vaccination (14-17, 18-21, 22-26 weeks), GA at time of delivery (28-32, 33-36, 37+ weeks), and infant birthweight. Analysis will include GMCs along with corresponding 95% confidence intervals ([Table 37](#), [Table 38](#), [Table 39](#), and [Table 40](#)).

Additionally, regression modelling will be employed to evaluate the association of log-transformed anti-PT antibody response with each of the stratified maternal cofactors defined previously, as well as with infant birthweight as a continuous variable. Separate models will be used for each analysis population and each cofactor. The analysis of variance model for a stratified cofactors is as follows,

$$\ln(titer) = \beta_0 + \beta_{1i}x_i + \varepsilon;$$

where  $\beta_0$  is the intercept,  $x_i$  is a categorical variable with  $i$  levels for a cofactor with  $i + 1$  levels,  $\beta_{1i}$  is the regression coefficient for each level of the covariate  $x_i$ , and  $\varepsilon$  is random error assumed to be normally distributed. The model will be constructed using reference cell coding; a single level of each cofactor will be used as the reference level and the parameter  $\beta_{1i}$  will be estimated for the remaining levels.

The model for the continuous cofactor of infant birthweight is as follows,

$$\ln(titer) = \alpha_0 + \alpha_1z + \varepsilon;$$

where  $\alpha_0$  is the intercept,  $\alpha_1$  is the regression coefficient,  $z$  is the continuous covariate, and  $\varepsilon$  is random error assumed to be normally distributed.

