**Table 16: Summary of Maternal Continuous Demographic and Baseline Characteristics by Treatment Group**

Variable	Statistic	BOOSTRIX (N=X)	Td (N=X)	All Subjects (N=X)
Maternal Age (years)	Mean	xx.x	xx.x	xx.x
	Standard Deviation	xx.x	xx.x	xx.x
	Median	xx.x	xx.x	xx.x
	Minimum	xx	xx	xx
Gestational Age at Vaccination (weeks)	Maximum	xx	xx	xx
	Mean			
	Standard Deviation			
	Median			
	Minimum			
	Maximum			

Note: N= Number of subjects in the Maternal Safety Population

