	One month after receipt of last dose of DTwP (approximately 18 weeks of age)	n			
		GMC (95% CI)			
		Median (Q1, Q3)			
		Min, Max			
	Change from prior to first to post last dose of DTwP	n			
		Median (Q1, Q3)			
		Min, Max			
	6 months of age	n			
		GMC (95% CI)			
		Median (Q1, Q3)			
		Min, Max			
	Change from prior to first dose of DTwP to 6 months of age	n			
		Median (Q1, Q3)			

Table 35: Multiplex Assays Stimulated Peripheral Blood Cells Results with 95% Confidence Intervals by Cytokine, Time Point, and Treatment Group -- Infant Intent-to-Treat Population (continued)

Cytokine	Time Point	Statistic	BOOSTRIX (N=X)	Td (N=X)	Difference
		Min, Max			

Note: N=Number of subjects in the Infant ITT Population  
n=Number of subjects with results available at time point

Table with similar format:

**Table 36: Multiplex Assays Stimulated Peripheral Blood Cells Results with 95% Confidence Intervals by Cytokine, Time Point, and Treatment Group -- Infant Per Protocol Population**

**Table 37: Serum IgG Anti-PT ELISA GMC Results with 95% Confidence Intervals at Delivery Stratified by Maternal Cofactors -- Maternal Intent-to-Treat Population**

Cofactor	n	GMC	95% CI
Maternal Age			
18-29 years old	x	x.x	(x.x, x.x)
30-39 years old			
Parity			
Primiparous			
Multiparous			
GA at Time of Vaccination			
14-17 weeks			
18-21 weeks			
22-26 weeks			
GA at Time of Delivery			
28-32 weeks			
33-36 weeks			
37 or more weeks			

Tables with similar format:

**Table 38: Serum IgG Anti-PT ELISA GMC Results with 95% Confidence Intervals at Delivery Stratified by Maternal Cofactors -- Maternal Per Protocol Population****Table 39: Serum IgG Anti-PT ELISA GMC Results with 95% Confidence Intervals at Birth Stratified by Maternal Cofactors -- Infant Intent-to-Treat Population****Table 40: Serum IgG Anti -PT ELISA GMC Results with 95% Confidence Intervals at Birth Stratified by Maternal Cofactors -- Infant Per Protocol Population**

**Table 41: Regression Analysis to Evaluate the Relationship of Anti-PT ELISA Response and Maternal Cofactors at Delivery -- Maternal Intent-to-Treat Population, BOOSTRIX**

Model Parameter	n	Parameter Estimate	SE	p-value	Ratio*	95% CI of Ratio
Maternal Age						
Intercept	x	xxx.x	xxx.x	0.xxx	NA	NA
18-29 years old (reference)	x	NA	NA	NA	NA	NA
30-39 years old	x	xxx.x	xxx.x	0.xxx	xxx.x	(xxx.x, xxx.x)
Parity						
Intercept						

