**16.2.11 Pregnancy Reports****Listing 18: 16.2.11.2: Pregnancy Reports – Gravida and Para**

Subject ID	Pregnancy Number	Gravida	Live Births									Spontaneous Abortion/ Miscarriage	Elective Abortions	Therapeutic Abortions	Major Congenital Anomaly with Previous Pregnancy?
			Extremely PB a	Very Early PB a	Early PB a	Late PB a	Early TB b	Full TB b	Late TB b	Post TB b	Still Births				

Note: Gravida includes the current pregnancy, para events do not.

a Preterm Birth  
b Term Birth

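### The cofactor models fit maternal age and both gestational ages only as bands; adding continuous terms would recover trend information at almost no cost

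*Protocol*

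**What the plan says.** Protocol 3.2.3 defines the cofactors for maternal and neonatal anti-PT as "Maternal age (18-29, 30-39 years old), parity (primiparous vs. multiparous), GA at time of vaccination (14-17, 18-21, 22-26 weeks", then GA at delivery in three bands (28-32, 33-36, 37 or more weeks) and infant birthweight. Protocol 11.4.3 and SAP 6.4 attach the bands to stratified summaries and add that the cofactors will be evaluated by regression.

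SAP 8.3.1 fixes the form of that regression. In the BOOSTRIX arm, log titer is modelled on "each of the stratified maternal cofactors defined previously, as well as with infant birthweight as a continuous variable". For the banded cofactors, "The model will be constructed using reference cell coding; a single level of each cofactor will be used as the reference level". Each model holds one cofactor: "Separate models will be used for each analysis population and each cofactor". The Table 41 shell confirms that the bands are the model parameters, with "18-29 years old (reference") as the reference row for age and the lowest band as the reference for each gestational age.

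The continuous values exist. Table 16 summarises maternal age in years and "Gestational Age at Vaccination (weeks"). Table 18 summarises GA at delivery in days. I found no reason given for the cut points and no continuous model planned for these three variables.

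**The concern.** A step model treats a woman vaccinated at 14 0/7 weeks like one vaccinated at 17 6/7, and treats 17 6/7 and 18 0/7 as different. Any trend inside a band is discarded, and a three-band variable also spends a second degree of freedom. The section is not uniform either: birthweight enters "as well as with infant birthweight as a continuous variable", while age and the two gestational ages do not.

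Timing of vaccination is the cofactor with most bearing on the rationale. Protocol 2.1.8 cites evidence that earlier vaccination may help and settles on the second trimester. The models use only the BOOSTRIX arm, at most 133 women, so a gradual trend over 14-26 weeks is the kind of association that banding could miss.

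**Working it through.** **Inputs.** Age 18-39 inclusive, taken as 18 to 40, cut at 30. GA at vaccination 14 0/7 to 26 6/7, taken as 14 to 27, cut at 18 and 22 (Protocol 5.1 and 3.2.3). BOOSTRIX arm n = 133 (Protocol 5.3.1); with the 15% exclusion of Protocol 11.2.2, 133 × 0.85 = 113. Two-sided alpha 0.05, which Protocol 11.2.3 states for Table 11 only and is assumed here. The distributions of age and GA are in neither document, so every loss below rests on an assumed shape.

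**The plan's nearest figure.** No power or precision is stated for the cofactor models. Table 10 gives maternal anti-PT at delivery as GMC 51, log SD 0.90, 95% CI 43.7 to 59.5 at n = 133. Check: 51 × exp(±1.978 × 0.90/√133) = 43.70 to 59.51. It reproduces.

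**Step 1: information lost for a linear trend.** Loss L = 1 − Var(band means)/Var(X). For a uniform X with band widths w and total width W, this is Σw³/W³.

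- GA at vaccination, uniform: (4³ + 4³ + 5³)/13³ = 253/2197 = 11.5%.
- Age, uniform: (12³ + 10³)/22³ = 2728/10648 = 25.6%.
- Age, normal with mean 25 and SD 5, truncated to 18-40 (numerical integration): 48.4%.

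Other truncated normals move these widely. Age gives 32% to 81% for means 22-30 and SDs 4-6. GA at vaccination gives 15% to 49% for means 16-24 and SDs 2-4. A late-skewed shape for GA at vaccination gives 16.5%. GA at delivery, cut at 33 and 37, loses 45% to 67% for roughly normal shapes with mean 38.5-39 and SD 1.5-2, because most births fall in the top band.

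**Step 2: what that does to power.** Choose the R² that gives one linear term 80% power: 0.0565 at n = 133 and 0.066 at n = 113. After banding, R²b = (1 − L)R² and the noncentrality is n·R²b/(1 − R²b). Example, age uniform at n = 113: R²b = 0.744 × 0.066 = 0.0491; noncentrality = 113 × 0.0491/0.9509 = 5.8; power 67%.

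| Cofactor and assumed shape | L | Power, planned banded test | Equivalent n of 133 |
|---|---|---|---|
| Age, uniform | 25.6% | 67% (1 df) | 99 |
| Age, normal 25, SD 5 | 48.4% | 51% (1 df) | 69 |
| GA at vaccination, uniform | 11.5% | 64-65% (2 df) | 118 |
| GA at vaccination, late-skewed | 16.5% | 62% (2 df) | 111 |

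Power is nearly the same at n = 113 and n = 133, because the effect is rescaled to 80% at each. The equivalent n is 133 × (1 − L).

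**Step 3: splitting the loss for GA at vaccination.** The lost information alone (1 df) takes 80% to 72-75%. The rest of the fall to 62-65% is the price of the second degree of freedom. Even with no information lost, a 2-df test of the same effect has 70% power.

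**The case against.** The strongest reply is that bands are legitimate when the shape is unknown. The loss exists only for a roughly linear relation; for a threshold, bands may lose less. Protocol 2.1.8 itself reports timing as contrasts between gestational windows, such as 27-30 against 31-36 weeks, and banded GMC ratios match that form. The bands are also part of the protocol's outcome measure, so replacing them would depart from it. All of this stands, and it is why continuous models should be added and the bands kept.

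The degrees-of-freedom argument also cuts both ways. A linear and a quadratic term tested jointly have about 70% power, not 80%. The 80% holds only if the linear term is the test and curvature is a check.

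SAP 6.4 says that the study is not powered for subgroup analyses, and SAP 6.8 that no specific null hypothesis is tested. The 80% benchmark is therefore a yardstick chosen here, not a target that the trial set. That limits the weight of the point but does not justify leaving recorded information unused.

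A reader might infer that parity will be misclassified, because Listing 18 notes that "Gravida includes the current pregnancy, para events do not", which would put a first-time mother at para 0. The documents do not support this. The note explains the columns of an obstetric-history listing, and nothing ties the parity variable in SAP 8.3.1 to that count.

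**Conclusion.** The point holds for three variables: maternal age, GA at vaccination and GA at delivery. Each is summarised as continuous and modelled only in bands. If the relation with log anti-PT is roughly linear, the planned models are less sensitive than the data allow. Under the shapes shown, power falls from 80% to about 62-65% for GA at vaccination and to 51-67% for age. More concentrated distributions would lose more.

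A reader might infer a fixed percentage lost across the exploratory associations in general. The documents do not support that. They give no distribution for age or GA, the losses differ by cofactor, and parity (two-level), birthweight (continuous), breast milk and cytokine analyses lose nothing in this way. The consequence is small: the analysis is exploratory, and no primary, secondary or safety result changes.

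**What to change.** In SAP 8.3.1 and Tables 41-44, add models with maternal age (per 5 years), GA at vaccination (per week, computed from days) and GA at delivery (per week, computed from days) as continuous terms. Report the GMC ratio per unit with its 95% CI from the linear model, and fit a quadratic term for each as a curvature check. Keep the protocol-defined bands in Tables 37-40 and keep the categorical models, so that the outcome measure in Protocol 3.2.3 is still delivered as written.

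The cost is SAP wording and extra rows in four shells, with no new data: three further models in each of Tables 41-44, or 12 in all, plus the curvature checks. The downside is a few more unadjusted exploratory results and a linearity assumption, which the quadratic term tests. The change should be made before database lock, by when Protocol 11.4 requires the SAP to be final.

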4. STUDY DESIGN

This is a phase II, single center, randomized, double-blind, active-controlled study in which 200 healthy pregnant women, ages 18 through 39 years, inclusive, will be randomly allocated in a 2:1 ratio to receive either Tdap (BOOSTRIX) or Td at 14 0/7 weeks through 26 6/7 weeks estimated GA. After signing an informed consent form (ICF), all subjects will undergo a review of current and past medical history, current and prior medication use, and recent vaccination history. A physical examination performed as part of routine antenatal care or a study-specific brief exam may be used to determine eligibility. For the fetuses of pregnant subjects, GA will be established by ultrasound, whenever possible, in combination with date of last menstrual period (LMP), when available, and fundal height.

Eligibility will be confirmed, and the subject will be enrolled in the study. Each subject will receive prenatal care consistent with national guidelines and with local standards as practiced by clinicians caring for pregnant women and delivering neonates in the study area. In Mali, this includes hemoglobin, sickle cell test, Rh group, HIV, syphilis, toxoplasmosis, and rubella serology and urine glucose and protein at the first presentation for antenatal care, urine albumin and glucose at each subsequent visit and ultrasound at 22 and 32 weeks gestation.

At the time of randomization to vaccine allocation, women will also be randomized to a schedule of postpartum visits for specimen collection. All women-infant pairs will have specimens collected at birth, at 6 weeks after delivery, and at 6 months after delivery. In addition, women-infant pairs will be allocated in a 1:1 ratio to have specimen collections at one month following the first dose of DTwP (approximately 10 weeks of age), or at one month following the third dose of DTwP (approximately 18 weeks of age). Thus, pregnant subjects will typically have 7 clinic visits (only 6 if delivery occurs before the first visit after vaccination, on Day 31): 3 antenatal visits (Screening Visit, Study Day 1 and Study Day 31, unless delivery occurs first), 1 visit at the time of delivery, and 3 postpartum visits – at 6 weeks, at 10 or 18 weeks postpartum, and a final visit 6 months postpartum. The maternal subject will also undergo 2 home visits after vaccination to assess her health status (Days 4 and 8).

Infants born to the pregnant subjects will have 4 study visits: at birth, at approximately 6 weeks of age (day of first DTwP), at approximately 10 or 18 weeks of age (one month after first or third dose of DTwP, respectively), and at 6 months of age.

Blood and colostrum/breast milk samples for immunologic assessments will be collected as described below:

- Pregnant subject: approximately 30 mL of blood will be collected on Study Day 1 (prior to vaccination), Study Day 31 (one month after vaccination), at delivery, and at 6 months postpartum in all women.
- Infants: up to 30 mL of umbilical cord blood will be collected at delivery and 5 mL peripheral blood will be collected at 6 weeks (prior to first dose of DTwP), either the 10-

week or 18-week (per randomized study schedule), and 6 months of age in all infants. If cord blood cannot be obtained, 2-5 mL of peripheral blood will be collected by venipuncture within 72 hours of birth, before discharge, when possible. Cord blood is preferred over venipuncture.

- At delivery, and at the 6-week, either the 10-week or 18-week (per randomized study schedule), and the 6-month postpartum visit, a 10-20mL sample of colostrum or breast milk will be collected. When possible, the first breast milk or colostrum collection will occur while the mother and baby are admitted for delivery and postpartum care. When not possible, it may be collected any time within the first 4 days of life.

Safety will be monitored from the time of signing of the ICF until trial termination.

For additional details on study procedures and evaluations and study schedule by type of visit or study visits/days, see [Sections 7](#) and [8](#) and [Appendix A](#).

5. STUDY ENROLLMENT AND WITHDRAWAL

Subject Inclusion and Exclusion Criteria must be confirmed by a study clinician licensed to make medical diagnoses.

No exemptions are granted on Subject Inclusion/Exclusion Criteria in DMID-sponsored studies. Questions about eligibility will be directed toward the DMID Medical Officer.

5.1. Subject Inclusion Criteria

Prospective subjects must meet all of the following inclusion criteria to be considered eligible for enrollment:

1. Healthy pregnant woman 18-39 years of age, inclusive.
2. Singleton fetus, with estimated gestational age of 14 0/7 through 26 6/7 weeks gestation, inclusive, on the day of study vaccination.
3. Provide written consent after the nature of the study has been explained according to local regulatory requirements and prior to any study procedures.¹
4. In good health as determined by medical history, targeted physical examination^{2,3}, vital signs^{4,5,6}, and clinical judgment of the investigator.

¹ Prior to obtaining individual informed consent for each subject, the investigators will obtain community consent by discussing the trial with all the appropriate local groups, as necessary, to obtain permission to approach the subjects. Written, informed consent for participation in the trial will be obtained by the investigators from all individual subjects. The consent forms will be written in French, the official language of Mali, and will be translated into Bambara, the most prevalent of the local languages, and recorded on audiotape.

² if indicated based on medical history, to evaluate acute or currently ongoing chronic medical diagnoses or conditions that would affect the assessment of eligibility and safety of subjects. Chronic medical diagnoses or conditions being actively managed must be within acceptable limits in the last 180 days. Any prescription change that is due to change of health care provider, insurance company, etc., or that is done for financial reasons, as long as in the same class of medication, will not be considered a deviation of this inclusion criterion. Any change in prescription medication due to improvement of a disease outcome, as determined by the site principal investigator or appropriate sub-investigator, will not be considered a deviation of this inclusion criterion. Subjects may be on chronic or as needed (prn) medications if, in the opinion of the site principal investigator or appropriate sub-investigator, they pose no additional risk to subject safety or assessment of reactogenicity and immunogenicity and do not indicate a worsening of medical diagnosis or condition. Similarly, medication changes subsequent to enrollment and the study vaccination are acceptable provided the subject is asymptomatic, condition stable, and there is no additional risk to the subject or interference with the evaluation of responses to the study vaccination.

³ Physical examination performed as part of routine antenatal care of a study-specific brief exam may be used to determine eligibility.

⁴ Oral temperature less than 37.8°C.

⁵ Pulse 55 to 100 bpm, inclusive.

⁶ Systolic blood pressure 90 to 140 mm Hg, inclusive. Diastolic blood pressure 55 to 90 mm Hg, inclusive.

5. Ability to comprehend and comply with all study procedures, as determined by the investigator determining eligibility, and availability for follow-up.
6. Willing to allow study staff to gather pertinent medical information, including pregnancy outcome data and medical information about her infant.

5.2. Subject Exclusion Criteria

Prospective subjects must not meet any of the following exclusion criteria to be considered eligible for enrollment:

1. History of illness or an ongoing illness that, in the opinion of the investigator, may pose additional risk to the subject or her fetus if she participates in the study.
2. Infection requiring systemic antibiotics or antiviral treatment within the 7 days prior to study vaccination.
3. Fever (oral temperature $\geq 37.8^{\circ}\text{C}/100.0^{\circ}\text{F}$) or other acute illness within 3 days prior to study vaccination.⁷
4. Known active neoplastic disease⁸, anticancer chemotherapy, or radiation therapy (cytotoxic) within 3 years prior to study vaccination.
5. History of any hematologic malignancy at any time.
6. A history of a serious adverse event following previous immunizations (e.g., Bell's Palsy, Guillain-Barre Syndrome, encephalopathy), or history of progressive neurologic disorders.
7. Known or suspected disease that impairs the immune system including known or suspected HIV infection or HIV-related disease.
8. Receipt of immunosuppressive therapy.⁹
9. Known hepatitis B or hepatitis C infection, by history or medical record.

⁷ An acute illness which is nearly resolved with only minor residual symptoms remaining is allowable if, in the opinion of the site principal investigator or appropriate sub-investigator, the residual symptoms will not interfere with the ability to assess safety parameters as required by the protocol.

⁸ excluding non-melanoma skin cancer.

⁹ including long-term use of glucocorticoids: oral, inhaled, intranasal or parenteral prednisone ≥ 20 mg/day or equivalent for more than 2 weeks within the 30 days prior to enrollment. Use of topical corticosteroids is allowed.

10. Behavioral or cognitive impairment or psychiatric disease¹⁰ that, in the opinion of the investigator, may interfere with the subject's ability to participate in the trial.
11. Have a history of alcohol or drug abuse within 5 years prior to study vaccination.¹¹
12. Known hypersensitivity or allergy to any component of the study vaccine (formaldehyde, alum).
13. History of severe allergic reaction (e.g., anaphylaxis) after a previous dose of BOOSTRIX or any other vaccine directed against tetanus, diphtheria, or pertussis.
14. Receipt or planned receipt of any live licensed vaccine within 30 days before or after vaccination or any inactivated licensed vaccine within 14 days before or after vaccination.
15. Receipt of immunoglobulin (except RhoGAM, which is allowed) or other blood products within 90 days prior to study vaccination.
16. Receipt of an experimental agent or device within 30 days prior to vaccination, or the expected receipt of an experimental agent¹² (other than BOOSTRIX) during this trial-reporting period.
17. High risk for serious obstetrical complication (refer to ACOG Practice Bulletins for definitions, as necessary).¹³
18. Pregnant with a fetus with a known or suspected major congenital¹⁴ anomaly or genetic abnormality.
19. Study personnel or immediate family members (brother, sister, child, parent) or the spouse of study personnel.

¹⁰ includes hospitalization for psychiatric illness, suicide attempt, or confinement for danger to self or others within 10 years prior to study vaccination.

¹¹ that is believed by the site investigator to potentially interfere with the subject's ability to participate in the study.

¹² Experimental agents include vaccines, drugs, biologics, devices, blood products, and medications. Subjects who have received a licensed product, as a subject in a clinical trial, within 30 days prior to vaccination or who are expecting to enroll in such a trial during the study period will also be excluded. Observational studies, surveys, and other studies that do not involve experimental agents or devices are allowed.

¹³ including the following: (a)gestational hypertension (well controlled history of essential or gestational hypertension, as evidenced by normal BPs as defined above, is allowed), (b)gestational diabetes not controlled by diet and exercise (the use of insulin or glyburide to control gDM, at the time of enrollment, is exclusionary), (c)current pre-eclampsia or eclampsia, (d)known current multiple gestation, (e)history of preterm delivery before EGA 35 weeks 0 days or current preterm labor, and/or (f)known intrauterine fetal growth restriction (defined as ultrasound confirmation of an estimated fetal weight that is less than the 10th percentile for gestational age).

¹⁴ Congenital anomalies and definitions of major congenital anomalies are discussed in detail in [Section 9.1](#) under Assessment of Safety.

